11.2 Study Hypotheses

This Phase II study is not designed to test a formal null hypothesis. Rather, it is intended to obtain sufficient data to obtain meaningful estimates of the immune response induced by this vaccine and to uncover any safety issues that occur at a sufficiently high rate that they might be observed in a study of this size. The sample size facilitates formal testing of selected hypotheses as discussed in [Section 11.4.3](#), along with the probability of observing safety outcomes and the precision of immunogenicity outcomes.

11.3 Study Outcome Measures

Please refer to Study Outcome Measures outlined in [Section 3.2](#).

11.4 Sample Size Considerations

Please refer to Study Design outlined in [Section 4](#).

11.4.1 Study Population

The study population for this clinical trial includes males and non-pregnant females, 19 to 50 years of age, who are in good health and meet all eligibility criteria. The subjects will be recruited from the general population at each of the participating VTEU sites that have substantial experience conducting large influenza vaccine studies.

11.4.2 Subject Enrollment and Follow-up

Based on the accrual rates observed in similar studies, it seems reasonable to expect that the participating VTEUs will be able to enroll this trial in a timely fashion. In previous DMID trials, 7 VTEUs recruited 388 healthy subjects, 19 to 64 years of age, in 14 weeks. Prior experience suggests up to 15% of subjects (approximately 10% of subjects assigned to the 4-month interval and 5% of subjects assigned to the 21-day interval), 19 to 64 years of age, may be excluded from the per protocol (PP) analysis for the primary immunogenicity outcome either because they did not receive the second study vaccination, were lost-to-follow-up, or because they had a protocol deviation requiring their exclusion from the PP analysis.

Follow-up will consist of 2 segments. The first encompasses the core data for this trial and will consist of results for all study visits through approximately 21 days after the last study vaccination. The second segment consists of a 6-month immunogenicity assessment and follow-up safety assessments through approximately 12 months after the last study vaccination.

11.4.3 Sample Size

This study is planned to enroll up to 180 subjects. The sample size for this study was selected to obtain preliminary estimates in a time critical manner. While this study is not designed to test any specific null hypothesis, the following illustrates the precision and power that are available for select estimates and comparisons of interest.

[Table 12](#) indicates the probability of observing one or more safety events, such as solicited injection site or systemic reactogenicity events or an unsolicited non-serious AE of a particular type for a single treatment arm (N=30), or in the trial as a whole (N=180).

Table 12: Power (%) to Detect Safety Events

Event Frequency	N=30	N=180
≥10% Very Common	95	>99
≥1% Common	26	83
≥0.1% Uncommon	2	16
≥0.01% Rare	<1	1

Binomial confidence intervals (CI) are widest (have the least precision) when the response rate is 50%. [Table 13](#) is presented to indicate the worst-case scenario for precision of observed exact (Clopper-Pearson) binomial confidence intervals.

Table 13: Precision of Binomial Confidence Intervals

N	95% CI
30	31-69
180	42-58

[Table 14](#) illustrates the minimum detectable differences in the proportion of subjects responding (e.g. attaining seroconversion or a titer $\geq 1:40$) between any two treatment arms (N=30) using a two-sided Likelihood Ratio Test and $\alpha = 0.05$. It is assumed that up to 10% of subjects (N=3) will be excluded from the per protocol analysis. Seroconversion rates of 10% to 50% are considered.

Table 14: Minimum Detectable Difference in Proportion Responders

N per Group	Proportion Responders in Comparator Group A	80% Power	
		Minimal Detectable Difference	Proportion Responders in Comparator Group B
N=27	0.10	0.32	0.42
	0.20	0.35	0.55
	0.30	0.38	0.68
	0.40	0.37	0.77
	0.50	0.34	0.84

11.5 Planned Interim Analyses

A DSMB will be convened by DMID to review study progress and subject, clinical, safety, reactogenicity, and immunogenicity data as described in [Section 9.6.2](#).

A set of “topline” immunogenicity and safety tables produced on an expedited timeline will be prepared as described in [Section 11.6](#); though this report will be released while subjects remain in this trial for long-term safety follow-up, it will be considered the final analysis of these data.

Emergent public health needs may dictate additional interim safety, reactogenicity and/or immunogenicity analyses be performed on available information at any time during this trial. If this occurs, immunogenicity data will be analyzed as results are available from Southern Research.

Interim analyses will be used only to terminate this trial in the event that unanticipated safety events deemed to be of sufficient concern require such action by the sponsor. These assessments

will not be made on the basis of testing a formal statistical hypothesis; therefore, p-value adjustment will not be made to any analyses.

11.5.1 Interim Safety Review

An interim safety review may include enrollment and demographic information, medical history, concomitant medications, physical assessments, clinical laboratory values, dosing compliance, and solicited and unsolicited AE/SAEs. Additional data may be requested by the DSMB, and interim statistical reports may be generated as deemed necessary and appropriate by DMID. The DSMB may receive data in aggregate and presented by treatment arm. The DSMB may also be provided with expected and observed rates of the expected AEs in an unblinded fashion, and may request the treatment assignment be unblinded for an individual subject if required for safety assessment. The DSMB will review grouped and unblinded data in the closed session only. The DSMB will meet and review this data at trial-specific time frames or ad hoc as needed during this trial as defined in the DSMB charter. As an outcome of each review/meeting, the DSMB will make a recommendation as to the advisability of proceeding with study vaccinations, as applicable, and to continue, modify or terminate this trial.

The interim safety reports generated for the DSMB are not intended to be published; they will be used only for informing emergency preparedness.

Additionally, this trial will be monitored to determine if any of the halting rules described in [Section 9.5](#) are met.

11.5.2 Interim Immunogenicity Review

Should emergent public health needs dictate interim immunogenicity review, immune responses will be summarized in terms of strain-specific 2013 and 2017 A/H7N9 HAI and Neut antibody titers and the relationship to study vaccine dosage, adjuvant use and study vaccination schedule. It is anticipated that all analyses will be carried out in parallel for both assays, but reports may be prepared separately for HAIs and Neuts if results are available on different timelines. Interim analyses will focus on rates of titers $\geq 1:40$, seroconversion (defined as either a pre-vaccination titer $< 1:10$ and a post-vaccination titer $\geq 1:40$ or a pre-vaccination titer $\geq 1:10$ and a minimum four-fold rise in post-vaccination titer) and GMTs, along with corresponding 95% CIs. No formal hypothesis testing will be included in the interim analysis, and interim results will not have impact on conduct of this trial.

Any immunogenicity reports would be provided by the SDCC to the DMID Scientific Lead, DMID Clinical Project Manager and DSMB. Reports will include data summarized by unblinded

treatment arm, but the presentation will be in a format that prevents inadvertent unblinding of any individual subject.

There is no plan to halt this trial prior to full enrollment and completion of all follow-up visits based on any interim immunogenicity results.

11.6 Final Analysis Plan

Clinical, safety and reactogenicity data through approximately 180 days after the last study vaccination will represent the primary clinical database for this trial. Once the last subject completes the visit that occurs approximately 180 days after the second study vaccination and all HAI and Neut results are received, a “topline” subset of the immunogenicity and safety tables will be provided to DMID on an expedited timeline. These analyses may be made available to the sponsor for planning subsequent trials and to the lead PI for publication. These analyses will not be used to make any decisions concerning the conduct of this trial. As it is anticipated that subjects will remain in long-term safety and immunogenicity follow-up at the time of these analyses, blinded site investigators and DMID Medical Monitors not involved in the analysis, publication or clinical study report (CSR) preparation will be responsible for assessing SAEs and MAAEs, including NOCMCs and PIMMCs, until all subjects have completed the final follow-up visit. All analyses of data included in the topline tables for early release will be considered the final analysis of these data, and also included in the final CSR.

Analysis of exploratory immunogenicity endpoints, including cellular immunology and additional serological assays, may be performed and released as the data are available from the research laboratories. Any such analyses would be considered the final analysis for the endpoint, and included in the CSR.

The final CSR will be completed after the last subject’s last visit is completed, and the final clinical database, including all long-term safety follow-up data, is cleaned, monitored and locked. Additional exploratory immunogenicity endpoint data not available at the time of CSR preparation may be included in an addendum to the CSR.

A formal statistical analysis plan (SAP) will be developed and finalized prior to unblinding for any analysis, which defines the analyses to be included in the topline tables and final CSR.

11.6.1 Analysis Populations

The Safety Analysis population includes all subjects who received at least one dose of study vaccine.

The modified intent-to-treat (mITT) population includes all subjects who received at least one dose of study vaccine and contributed both pre- and at least one post-study vaccination venous blood samples for HAI and Neut antibody assays for which valid results were reported. For analyses using the mITT population, subjects will be grouped based on their randomized treatment arm.

The PP population includes all subjects in the mITT subset with the following exclusions:

- Data from all available visits for subjects found to be ineligible at baseline.
- Data from all visits subsequent to major protocol deviations, such as:
 - Second study vaccination not received,
 - Second study vaccination received out of window,
 - Receipt of non-study licensed, live vaccine within 30 days before or after each study vaccination,
 - Receipt of non-study licensed, inactivated vaccine within 14 days before or after each study vaccination,
 - Receipt of immunosuppressive therapy (e.g., corticosteroids) within 30 days before or after each study vaccination.
- Data from any visit that occurs substantially out of window.

For analyses using the PP population, subjects will be grouped based on study vaccinations received.

11.6.2 Safety Data

Summaries and analysis of safety data will be presented for the Safety Analysis Population. All summaries and analyses will be presented for all subjects.

Solicited AEs will be summarized by severity for each day after each study vaccination (Days 1-8 post each study vaccination) and as the maximum severity over all 8 days. Additionally, solicited AEs will be analyzed by taking the most severe response over the follow-up period, dichotomizing into a binary variable (none versus mild, moderate or severe) and using standard techniques, such as exact CIs, to summarize the proportion of subjects reporting each symptom, any injection site symptom and any systemic symptom. Summaries of solicited AEs will be presented separately for each study vaccination as well as overall study vaccinations by

treatment arm. The proportion of subjects reporting symptoms may be compared between treatment arms using Chi-square or Fisher's exact test. The proportion of subjects reporting solicited symptoms between the different study vaccinations (i.e., first and second) will be compared using McNemar's test.

Unsolicited AEs will be coded by Medical Dictionary for Regulatory Activities (MedDRA[®]) for preferred term and system organ class (SOC). The numbers of SAEs and MAAEs, including NOCMCs and PIMMCs, are likely to be small in this trial and will be reported by detailed listings showing the event description, MedDRA[®] preferred term and SOC, relevant dates (study vaccinations and AEs), severity, relatedness, and outcome for each event. Non-serious unsolicited AEs will be summarized as number and percentage of subjects reporting at least one event in each MedDRA[®] preferred term and SOC, cross-tabulated by severity and relationship to study product. Additionally, the proportion of subjects and exact 95% CIs of AEs in aggregate and by MedDRA[®] categories will be computed.

Clinical laboratory data will be summarized by severity for each visit and as the maximum over all post-study vaccination visits. Graphical presentations may include box plots.

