As of November 22, 2015 (per the GSK AS03 Adjuvant Investigator's Brochure dated February 2016), data are available for 56 GSK-sponsored clinical trials of AS03-adjuvanted monovalent pandemic vaccines manufactured by GSK. More than 18,000 adult (age ≥ 18 years) and 6,900 pediatric (6 months to 17 years old) clinical trial participants have received at least one dose of a GSK-manufactured, AS03-adjuvanted monovalent pandemic influenza vaccine. Clinical data collected by GSK as of November 22, 2015, suggest that inactivated monovalent (pre)pandemic influenza virus antigens adjuvanted with AS03 have generally acceptable safety and benefit/risk profiles, though the incidence rates of solicited injection site and systemic AEs are higher with AS03-adjuvanted antigens than with antigen alone, a licensed IIV3 or placebo. Some unsolicited AEs (e.g., insomnia, dizziness, cystitis) were associated with a higher relative risk among AS03-adjuvanted H5N1 recipients in contrast to Fluarix[®] or placebo recipients.

The information and guidance that follow are based on pre-clinical and clinical study results for GSK-manufactured AS03-adjuvanted monovalent pandemic vaccines, post-marketing safety surveillance data seen with unadjuvanted, IIV3s and (in the case of the A/H1N1 vaccines) post-marketing safety surveillance data seen to date for both Pandemrix[™] and Arepanrix[™] H1N1 vaccines.

The reactogenicity profile in humans of GSK-manufactured AS03-adjuvanted vaccines is primarily associated with the adjuvant. The incidence and severity of injection site redness, swelling and pain at the injection site in recipients of AS03-adjuvanted vaccines are increased relative to monovalent pandemic influenza antigen alone, a licensed IIV3 or placebo. There is no increase in injection site and systemic reactogenicity events in recipients of AS03-adjuvanted vaccines after a second dose of vaccine relative to the first when given 21 days apart. In young children (6 months to 6 years old), increased frequency of fever has been observed following a heterologous booster dose of adjuvanted vaccine administered 6 months after the primary series.

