9.3.1. Solicited Events and Symptoms

Systemic solicited adverse events were collected pre-vaccination, and systemic and local solicited adverse events were collected at-least 20 minutes post-vaccination and then daily for 7 days after each vaccination and graded on a scale of 0 (absent), 1 (mild), 2 (moderate) and 3 (severe). Systemic events include fever, feverishness, fatigue, malaise, myalgia, arthralgia, headache, and nausea. The grading scale for systemic events, including quantitative grading for fever, is included in [Table 11](#). Local events include pruritus, ecchymosis, erythema, induration/swelling, pain, and tenderness. Ecchymosis, erythema, and induration are measured by both functional and measurement grading scales as defined in [Table 10](#).

When calculating the incidence of solicited events, each subject will be counted once at the highest severity following the applicable vaccination, and any repetitions will be ignored. For summaries presented separately for each vaccination, the denominator for percentages will be the number of subjects who received the respective vaccination with non-missing data for the event summarized. For summaries over all vaccinations the denominator will be the number of subjects who received at least one vaccination with non-missing data for the event summarized.

The number and percentage of subjects reporting at least one solicited adverse event of each severity will be summarized for each solicited symptom, any systemic symptom, any local symptom, and any symptoms. For each event the denominator is the number of subjects who received the applicable vaccination with non-missing data for the specific event. The 95% CI calculated using Clopper-Pearson methodology from a binomial distribution (SAS Proc Freq with a binomial option) will be presented ([Table 84](#), [Table 85](#), [Table 86](#)). Logistic regression models will be fit to estimate the effect of prime-boost combination (*PrimeBoost*), Boost dose (*BoostDose*), and interval between vaccinations (*Interval*) on the probability of reporting any local event or reporting any systemic event after either vaccination ([Table 87](#), [Table 88](#)). If statistically significant effects are observed in the model for local events or systemic events, then additional models will be fit for each individual event of that type.

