$$\text{logit}[P(\text{Event})] = \beta_0 + \beta_1 \times \text{PrimeBoost} + \beta_2 \times \text{BoostDose} + \beta_3 \times \text{Interval} + \beta_4 \times (\text{PrimeBoost} * \text{BoostDose}) + \beta_5 \times (\text{PrimeBoost} * \text{Interval}) + \varepsilon,$$

For each systemic and local event, any systemic event, any local event, and any solicited event, the maximum severity over 7 days after each vaccination will be summarized for the Safety population. The number and percentage of subjects reporting each event will be summarized by the maximum severity and study group, separately for each vaccination and over both vaccinations. For each event the denominator is the number of subjects who received the applicable vaccination with non-missing data for the specific event. The 95% CI calculated using Clopper-Pearson methodology from a binomial distribution (SAS Proc Freq with a binomial option) will be presented ([Table 89](#), [Table 90](#), [Table 91](#)).

The number of subjects reporting a solicited adverse event will be summarized for each day post vaccination for each vaccination and for both vaccinations combined both in a summary table ([Table 92](#), [Table 93](#), [Table 94](#)) and graphically in a bar chart ([Figure 26](#) and [Figure 27](#)). A comparison of the event rate for each study group between study vaccinations will be presented, including p-values from McNemar's test performed ([Table 95](#), [Table 96](#)).

Systemic and Local solicited events reported by subject will be presented in [Listing 11](#) and [Listing 12](#), sorted by subject ID, vaccination number, parameter, and study day.

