| | n | % (95% CI) | n | % (95% CI) | n | % (95% CI) | n | % (95% CI) | n | % (95% CI) | n | % (95% CI) | n | % (95% CI) |
| N = Number of subjects in the Safety Population who received any study vaccination; n = Number of subjects reporting event 95% CI estimated using the Clopper-Pearson exact method | | | | | | | | | | | | | | |

Tables with similar format:

Table 85: Number and Percentage of Subjects Experiencing Solicited Events with 95% Confidence Intervals by Symptom and Study Group (Safety Population) – Post Study Vaccination 1

[Footnote update] N = Number of subjects in the Safety Population who received the first study vaccination.

Table 86: Number and Percentage of Subjects Experiencing Solicited Events with 95% Confidence Intervals by Symptom and Study Group (Safety Population) – Post Study Vaccination 2

[Footnote update] N = Number of subjects in the Safety Population who received the second study vaccination.

Table 87: Logistic Regression Model to Evaluate the Relationship of Study Vaccination with Reporting Any Local Event Post Second Study Vaccination, Safety Population

[Implementation Note: If statistically significant effects (defined as p-value <0.05) are observed in the model for local events then this table should be repeated for additional models which will be fit for each individual local event. Any solicited local event grade 1 or higher reported within 7 days of study vaccination will count as a reported event.]

| Model Parameter | Parameter Category | Parameter Estimate | SE | p-value | Odds Ratio | 95%CI |
|-----------------|------------------------|--------------------|-------|---------|------------|-----------|
| Intercept | N/A | xxx.x | xxx.x | x.xxx | - | - |
| Prime-boost | Homologous (reference) | - | - | - | - | - |
| | Heterologous | xxx.x | xxx.x | x.xxx | xx.x | xx.x-xx.x |
| Boost Dose | 15 mcg (reference) | - | - | - | - | - |
| | 3.75 mcg + AS03 | xxx.x | xxx.x | x.xxx | xx.x | xx.x-xx.x |
| Interval | 21 days (reference) | - | - | - | - | - |
| | 120 days | xxx.x | xxx.x | x.xxx | xx.x | xx.x-xx.x |

N = XX (number of subjects in the Safety Population)

Table with similar format:

Table 88: Logistic Regression Model to Evaluate the Relationship of Study Vaccination with Reporting Any Systemic Event Post Second Study Vaccination, Safety Population

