Table 95: Number and Percentage of Subjects Experiencing Solicited Systemic Events for Study Vaccination 1 Compared with Study Vaccination 2 by Study Group– Safety Population

| | | Subjects with No Symptoms | Subjects with Mild or Greater Symptoms | Total Number of Subjects n (Percent) [p-value*] |
|---|--|---------------------------|--|---|
| Study Vaccination 1 vs Study Vaccination 2 | | | | |
| Group 1: 2013 3.75+AS03/ 2017 3.75+AS03 (D1-D22) (N=X) | Subjects with No Symptoms | x (%) | x (%) | x (%) |
| | Subjects with Mild or Greater Symptoms | x (%) | x (%) | x (%) |
| | Total Number of Subjects | x (%) | x (%) | x (100%) [0.xxx] |
| Group 2: 2013 3.75+AS03/ 2017 3.75+AS03 (D1-D121) (N=X) | Subjects with No Symptoms | x (%) | x (%) | x (%) |
| | Subjects with Mild or Greater Symptoms | x (%) | x (%) | x (%) |
| | Total Number of Subjects | x (%) | x (%) | x (100%) [0.xxx] |
| Group 3: 2013 3.75+AS03/ 2017 15 (D1-D121) (N=X) | Subjects with No Symptoms | x (%) | x (%) | x (%) |
| | Subjects with Mild or Greater Symptoms | x (%) | x (%) | x (%) |
| | Total Number of Subjects | x (%) | x (%) | x (100%) [0.xxx] |
| Group 4: 2017 3.75+AS03/ 2017 3.75+AS03 (D1-D22) (N=X) | Subjects with No Symptoms | x (%) | x (%) | x (%) |
| | Subjects with Mild or Greater Symptoms | x (%) | x (%) | x (%) |
| | Total Number of Subjects | x (%) | x (%) | x (100%) [0.xxx] |
| Group 5: | Subjects with No Symptoms | x (%) | x (%) | x (%) |
| | Subjects with Mild or Greater Symptoms | x (%) | x (%) | x (%) |

| | | Subjects with No Symptoms | Subjects with Mild or Greater Symptoms | Total Number of Subjects n (Percent) [p-value*] |
|--|--|---------------------------|--|---|
| 2017 3.75+AS03/ 2017 3.75+AS03 (D1-D121) (N=X) | Total Number of Subjects | x (%) | x (%) | x (100%) [0.xxx] |
| Group 6: 2017 3.75+AS03/ 2017 15 (D1-D121) (N=X) | Subjects with No Symptoms | x (%) | x (%) | x (%) |
| | Subjects with Mild or Greater Symptoms | x (%) | x (%) | x (%) |
| | Total Number of Subjects | x (%) | x (%) | x (100%) [0.xxx] |
| All Subjects (N=X) | Subjects with No Symptoms | x (%) | x (%) | x (%) |
| | Subjects with Mild or Greater Symptoms | x (%) | x (%) | x (%) |
| | Total Number of Subjects | x (%) | x (%) | x (100%) [0.xxx] |

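### Solicited reactions are graded 0-3, but every named test compares none with any, so no test can detect a shift in grade; add a severity analysis once the outcome window of Tables 87-88 is settled

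*Protocol*

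**What the plan says.** SAP 9.3.1 has each solicited reaction "graded on a scale of 0 (absent), 1 (mild), 2 (moderate) and 3 (severe"). Protocol 9.1 and SAP 4.5.1 both list frequency and severity as the basis for assessing safety. Solicited reactions are a primary safety outcome, worded as occurrence (Protocol 3.2.1, SAP 3.2.1).

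For analysis, Protocol 11.6.2 takes the most severe response over follow-up, "dichotomizing into a binary variable (none versus mild, moderate or severe"). The named tests are:

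- Between arms, optional: "The proportion of subjects reporting symptoms may be compared between treatment arms using Chi-square or" Fisher's exact test (Protocol 11.6.2).
- Dose 1 against dose 2: a comparison within each group, "including p-values from McNemar's test performed" (SAP 9.3.1). The Table 95 shell sets subjects without symptoms against "Subjects with Mild or Greater Symptoms".
- Logistic models for prime-boost combination, boost dose and interval, "on the probability of reporting any local event or reporting any systemic event after either vaccination" (SAP 9.3.1). The note to Table 87 fixes the cut: "Any solicited local event grade 1 or higher reported within 7 days of study vaccination will count as a reported event". The titles of Tables 87 and 88, however, refer to events after the second vaccination. Models for single symptoms are fitted only if the any-local or any-systemic model shows an effect at p<0.05.

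Severity is reported. Tables 89-91 give maximum grade by group, per vaccination and overall, with exact confidence intervals. Tables 92-94 and Figures 26-27 give grade by day. None of these carries a contrast between groups or between doses.

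**The concern.** The boost comparison sets 3.75 mcg with AS03 against 15 mcg without it (Groups 3 and 6). Protocol 2.3.1 says that "The incidence and severity of injection site redness, swelling and pain at the injection site in recipients of AS03-adjuvanted vaccines are increased" compared with antigen alone, so a difference may lie in grade as well as in rate. Each planned test scores a Grade 1 and a Grade 3 reaction alike, so only the rate is tested. A p-value or odds ratio from this plan could then show nothing while moderate and severe reactions differ. The any-local and any-systemic composites also decide whether the single-symptom models are run. A composite has a higher rate than any of its component symptoms, so it is the outcome on which a none-versus-any cut is most likely to carry little information.

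**Working it through.** **1. The plan's own power figure.** Protocol Table 14 (SAP Table 8) covers antibody responder rates: 27 v 27, two-sided likelihood ratio test, alpha 0.05. Exact binomial enumeration gives power of 0.816, 0.794, 0.805, 0.813 and 0.801 for 0.10 v 0.42, 0.20 v 0.55, 0.30 v 0.68, 0.40 v 0.77 and 0.50 v 0.84. The table is sound. There is no such figure for solicited reactions and no reaction rate anywhere, so the rates and severity splits below are assumptions.

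**2. A shift in grade only.** Keep the any-reaction rate equal in both arms and move reporters from 80/17/3 to 50/38/12 (mild/moderate/severe, %). With 57 v 57, none-versus-any has about 5% power, which is just alpha. At any-rates of 60, 80, 90 and 95%, an ordinal rank test has 20, 52, 75 and 86%, and a Grade 2 or higher cut has 68, 83, 89 and 92%. The blindness of the planned tests needs no ceiling; it holds at every rate.

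**3. A common odds shift.** The odds of grade k or higher in the comparison arm equal OR times those in the AS03 arm, for k = 1, 2, 3. Example: an any-rate of 80% has odds of 4; at OR 0.40 these become 1.6, a rate of 1.6/2.6 = 62%. Pooled sides (Groups 2+5 v 3+6) have 60 x 0.95 = 57 subjects after an assumed 5% loss. The binary test is Pearson's; the ordinal test is the tie-corrected Wilcoxon, the score test of the proportional-odds model. Each cell uses 100,000 simulated trials, and type I error was 4.9-5.5%. The efficiency of the cut is 3p(1-p)/(1 - sum of p_i cubed), where p is the proportion with no reaction and p_i the grade proportions. At 90% this is 3(0.1)(0.9)/(1 - 0.194) = 0.34.

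| AS03 arm, grades 0/1/2/3 (%) | Efficiency | OR 0.40, 57 v 57 | OR 0.33, 57 v 57 | OR 0.40, 30 v 30 | OR 0.33, 30 v 30 |
|---|---|---|---|---|---|
| 50/36/12/2 | 0.91 | 65.1 to 67.3 | 80.4 to 81.8 | 39.5 to 41.3 | 52.4 to 54.4 |
| 30/50/17/3 | 0.75 | 65.8 to 72.3 | 81.8 to 86.7 | 40.3 to 45.1 | 55.4 to 60.1 |
| 20/53/23/4 | 0.58 | 59.5 to 71.7 | 77.5 to 86.8 | 34.6 to 44.7 | 48.8 to 60.1 |
| 10/55/30/5 | 0.34 | 41.2 to 69.2 | 58.5 to 84.4 | 24.0 to 42.7 | 34.2 to 57.1 |

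Entries are power (%), binary to ordinal. The 30 v 30 columns matter because, with interactions kept and reference coding, the boost-dose coefficient compares one pair of groups. The gain there is about 2 to 23 points.

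**4. The outcome window.** Take 60 v 60, an AS03 prime with a 90% any-rate, and boosts at 60% (no AS03) and 90% (AS03). Reporters split 80/17/3 and 65/28/7, and within-subject correlation is 0.3-0.5.

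- After dose 2 only: binary 0.98, ordinal 0.99.
- After either dose: any-rates become 92-94% and 97-98%, so a 30-point difference shrinks to about 4. Binary power is 0.23-0.26 and ordinal 0.27-0.31.

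With boosts at 60% v 80% and an 80% prime, the post-dose-2 figures are 0.69 and 0.83. On the either-dose window, pooling costs far more than the cut.

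**5. Dose 1 against dose 2, n=30, correlation 0.5.** Each range runs from the exact to the asymptotic test.

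| Change in any-rate or grade | McNemar | Sign test on grade |
|---|---|---|
| 90% to 60% | 0.82-0.89 | 0.92-0.95 |
| 90% to 75% | 0.25-0.40 | 0.58-0.67 |
| 90% at both doses, reporters 65/28/7 to 45/40/15 | 0.01-0.05 | 0.26-0.33 |

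**6. Stability of the logistic model.** Its six coefficients fit six groups exactly, so a group with 30/30 reporters gives an infinite estimate. The chance of at least one such group is 1 - (1 - 0.90^30)^6 = 23% at a 90% rate and 77% at 95%.

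**The case against.** The strongest reply is that the trial tests no formal null hypothesis and its endpoint is occurrence, which none-versus-any matches. That stands as a reason to keep the binary results. It does not excuse the gap, because the SAP prints p-values and uses p<0.05 to decide which models are run.

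Three further points stand:

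- The size of the loss rests on an unstated rate. Protocol 2.3.1 gives only a direction. A reader might infer that AS03 in every prime puts the cut near its ceiling; the documents do not show that. On Tables 87-88 as titled, Groups 3 and 6 have had no AS03 at that dose, and for a large difference the cut costs almost nothing (0.98 v 0.99).
- Protocol 2.3.1 reports no increase in reactions after a second AS03 dose given 21 days after the first. That makes a rise from dose 1 to dose 2 less plausible in Groups 1 and 4. In Groups 3 and 6 McNemar already does well if the fall is large.
- The simulations in step 3 generate data under proportional odds, which favours the ordinal test. Step 2 does not, and there a Grade 2 or higher cut does better still.

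Also, Protocol 5.2.3 withholds dose 2 after certain Grade 3 reactions, so Tables 95-96 will hold few subjects with Grade 3 at dose 1. With those subjects dropped, a signed-rank test still led McNemar (46 v 30% to 65 v 41%, n=28, 90% rate).

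**Conclusion.** The point holds for the tests, not for the plan as a whole. Every named test uses none versus any and has power of about alpha against a shift in grade alone. Under a common odds ratio of 0.33-0.40 the loss at 57 v 57 is about 1-2 points at an assumed any-rate of 50%, 5-7 at 70%, 9-12 at 80% and 26-28 at 90%. Which of these applies cannot be settled from the documents.

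Two stronger readings are tempting and are not supported. One is that the trial would miss a clear difference in moderate or severe reactions: Tables 89-91 show maximum grade by group with exact intervals, so such a difference would be visible, though untested. The other is that the significance condition closes off the single symptoms: it stops only their logistic models, since per-symptom rates and grades are tabulated unconditionally and Protocol 11.6.2 also allows Chi-square or Fisher comparisons. This is a cheap improvement to secondary inference, and it comes second to settling the window.

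**What to change.** In SAP 9.3.1 and its table shells, before unblinding:

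1. Reconcile the outcome window: the text says either vaccination, the titles of Tables 87-88 say the second. Analyse boost effects on reactions after dose 2.
2. Beside the none-versus-any results, add a cumulative-logit model for maximum functional grade per vaccination, with the same terms. Pool Grades 2-3 if Grade 3 is sparse; use a Grade 2 or higher cut if proportional odds fails.
3. In Tables 95-96, add a dose 1 by dose 2 grade table for each group with a signed-rank or sign test, keeping McNemar.
4. Fit the per-symptom models without the significance condition.
5. Record the additions in SAP section 12.

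No new data are needed, and the SAS software already named will do. Protocol 11.6.2 offers its techniques as examples, so adding an analysis does not contradict it. The cost is a little more output, a proportional-odds assumption to check, and a common odds ratio to explain in the report.
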